6.3.2 Methods for Evaluation of Measurable Disease

All measurements should be taken and recorded in metric notation using a ruler or calipers. All baseline evaluations should be performed as closely as possible to the beginning of treatment and never more than 4 weeks before the beginning of the treatment.

The same method of assessment and the same technique should be used to characterize each identified and reported lesion at baseline and during follow-up. Imaging-based evaluation is preferred to evaluation by clinical examination unless the lesion(s) being followed cannot be imaged but are assessable by clinical exam.

Clinical lesions: Clinical lesions will only be considered measurable when they are superficial (e.g., skin nodules and palpable lymph nodes) and ≥ 10 mm diameter as assessed using calipers (e.g., skin nodules). In the case of skin lesions, documentation by color photography, including a ruler to estimate the size of the lesion, is recommended.

Chest x-ray: Lesions on chest x-ray are acceptable as measurable lesions when they are clearly defined and surrounded by aerated lung. However, CT is preferable.

Conventional CT and MRI: This guideline has defined measurability of lesions on CT scan based on the assumption that CT slice thickness is 5 mm or less. If CT scans have slice thickness greater than 5 mm, the minimum size for a measurable lesion should be twice the slice thickness. MRI is also acceptable in certain situations (e.g. for body scans).

Use of MRI remains a complex issue. MRI has excellent contrast, spatial, and temporal resolution; however, there are many image acquisition variables involved in MRI, which greatly impact image quality, lesion conspicuity, and measurement. Furthermore, the availability of MRI is variable globally. As with CT, if an MRI is performed, the technical specifications of the scanning sequences used should be optimized for the evaluation of the type and site of disease. Furthermore, as with CT, the modality used at follow-up should be the same as was used at baseline and the lesions should be measured/assessed on the same pulse sequence. It is beyond the scope of the RECIST guidelines to prescribe specific MRI pulse sequence parameters for all scanners, body parts, and diseases. Ideally, the same type of scanner should be used and the image acquisition protocol should be followed as closely as possible to prior scans. Body scans should be performed with breath-hold scanning techniques, if possible.

PET-CT: At present, the low dose or attenuation correction CT portion of a combined PET-CT is not always of optimal diagnostic CT quality for use with RECIST measurements. However, if the site can document that the CT performed as part of a PET-CT is of identical diagnostic quality to a diagnostic CT (with IV and oral contrast), then the CT portion of the PET-CT can be used for RECIST measurements and can be used interchangeably with conventional CT in accurately

measuring cancer lesions over time. Note, however, that the PET portion of the CT introduces additional data which may bias an investigator if it is not routinely or serially performed.

Ultrasound: Ultrasound is not useful in assessment of lesion size and should not be used as a method of measurement. Ultrasound examinations cannot be reproduced in their entirety for independent review at a later date and, because they are operator dependent, it cannot be guaranteed that the same technique and measurements will be taken from one assessment to the next. If new lesions are identified by ultrasound in the course of the study, confirmation by CT or MRI is advised. If there is concern about radiation exposure at CT, MRI may be used instead of CT in selected instances.

Endoscopy, Laparoscopy: The utilization of these techniques for objective tumor evaluation is not advised. However, such techniques may be useful to confirm complete pathological response when biopsies are obtained or to determine relapse in trials where recurrence following complete response (CR) or surgical resection is an endpoint.

Tumor markers: Tumor markers alone cannot be used to assess response. If markers are initially above the upper normal limit, they must normalize for a patient to be considered in complete clinical response. Specific guidelines for both CA-125 response (in recurrent ovarian cancer) and PSA response (in recurrent prostate cancer) have been published.($\frac{40-42}{2}$) In addition, the Gynecologic Cancer Intergroup has developed CA-125 progression criteria which are to be integrated with objective tumor assessment for use in first-line trials in ovarian cancer.($\frac{43}{2}$)

Cytology, Histology: These techniques can be used to differentiate between partial responses (PR) and complete responses (CR) in rare cases (e.g., residual lesions in tumor types, such as germ cell tumors, where known residual benign tumors can remain).

The cytological confirmation of the neoplastic origin of any effusion that appears or worsens during treatment when the measurable tumor has met criteria for response or stable disease is mandatory to differentiate between response or stable disease (an effusion may be a side effect of the treatment) and progressive disease.

FDG-PET: While FDG-PET response assessments need additional study, it is sometimes reasonable to incorporate the use of FDG-PET scanning to complement CT scanning in assessment of progression (particularly possible 'new' disease). New lesions on the basis of FDG-PET imaging can be identified according to the following algorithm:

- a. Negative FDG-PET at baseline, with a positive FDG-PET at follow-up is a sign of PD based on a new lesion.
- b. No FDG-PET at baseline and a positive FDG-PET at follow-up: If the positive FDG-PET at follow-up corresponds to a new site of disease confirmed by CT, this is PD. If the positive FDG-PET at follow-up is not confirmed as a new site of disease on CT, additional follow-up CT scans are needed to determine if there is truly progression occurring at that site (if so, the date of PD will be the date of the initial abnormal FDG-PET scan). If the positive FDG-PET at follow-up corresponds to a pre-existing site of disease on CT that is not progressing on the basis of the anatomic images, this is not PD.
- c. FDG-PET may be used to upgrade a response to a CR in a manner similar to a biopsy in cases where a residual radiographic abnormality is thought to represent fibrosis or scarring. The use of FDG-PET in this circumstance should be prospectively described

in the protocol and supported by disease-specific medical literature for the indication. However, it must be acknowledged that both approaches may lead to false positive CR due to limitations of FDG-PET and biopsy resolution/sensitivity.

Note: A 'positive' FDG-PET scan lesion means one which is FDG avid with an uptake greater than twice that of the surrounding tissue on the attenuation corrected image.

6.3.3 Response Criteria

6.3.3.1 Evaluation of Target Lesions

Complete Response (CR): Disappearance of all target lesions. Any pathological lymph nodes (whether target or non-target) must have reduction in short axis to <10 mm.

Partial Response (PR): At least a 30% decrease in the sum of the diameters of target lesions, taking as reference the baseline sum of diameters.

Progressive Disease (PD): At least a 20% increase in the sum of the diameters of target lesions, taking as reference the smallest sum on study (this includes the baseline sum if that is the smallest on study). In addition to the relative increase of 20%, the sum must also demonstrate an absolute increase of at least 5 mm. (Note: the appearance of one or more new lesions is also considered progressions).

Stable Disease (SD): Neither sufficient shrinkage to qualify for PR nor sufficient increase to qualify for PD, taking as reference the smallest sum of diameters while on study.

6.3.3.2 Evaluation of Non-Target Lesions

Complete Response (CR): Disappearance of all non-target lesions and normalization of tumor marker level. All lymph nodes must be non-pathological in size (<10 mm short axis).

Note: If tumor markers are initially above the upper normal limit, they must normalize for a patient to be considered in complete clinical response.

Non-CR/Non-PD: Persistence of one or more non-target lesion(s) and/or maintenance of tumor marker level above the normal limits.

Progressive Disease (PD): Appearance of one or more new lesions and/or *unequivocal progression* of existing non-target lesions. *Unequivocal progression* should not normally trump target lesion status. It must be representative of overall disease status change, not a single lesion increase.

Although a clear progression of "non-target" lesions only is exceptional, the opinion of the treating physician should prevail in such circumstances, and the progression status should be confirmed at a later time by the review panel (or Principal Investigator).

6.3.3.3 Evaluation of Best Overall Response

The best overall response is the best response recorded from the start of the treatment until disease progression/recurrence (taking as reference for progressive disease the smallest measurements recorded since the treatment started). The patient's best response assignment will depend on the achievement of both measurement and confirmation criteria.

Target Lesions	Non-Target Lesions	New Lesions	Overall Response	Best Overall Response when Confirmation is Required*
CR	CR	No	CR	≥4 wks. Confirmation**
CR	Non- CR/Non-PD	No	PR	
CR	Not evaluated	No	PR	>4 wks. Confirmation**
PR	Non- CR/Non- PD/not evaluated	No	PR	
SD	Non- CR/Non- PD/not evaluated	No	SD	Documented at least once ≥4 wks. from baseline**
PD	Any	Yes or No	PD	
Any	PD***	Yes or No	PD	no prior SD, PR or CR
Any	Any	Yes	PD	

For Patients with Measurable Disease	(i.e., Target Disease)
--------------------------------------	------------------------

new lesion.

** Only for non-randomized trials with response as primary endpoint.

In exceptional circumstances, unequivocal progression in non-target *** lesions may be accepted as disease progression.

Note: Patients with a global deterioration of health status requiring discontinuation of treatment without objective evidence of disease progression at that time should be reported as "symptomatic deterioration." Every effort should be made to document the objective progression even after discontinuation of treatment.

New Lesions	Overall Response	
No	CR	
No	Non-CR/non-PD*	
No	not evaluated	
Yes or No	PD	
Yes	PD	
	No No No Yes or No	

For Patients with Non-Measurable Disease (i.e., Non-Target Disease)

* 'Non-CR/non-PD' is preferred over 'stable disease' for non-target disease since SD is increasingly used as an endpoint for assessment of efficacy in some trials so to assign this category when no lesions can be measured is not advised

6.3.4 Duration of Response

Duration of overall response: The duration of overall response is measured from the time measurement criteria are met for CR or PR (whichever is first recorded) until the first date that recurrent or progressive disease is objectively documented (taking as reference for progressive disease the smallest measurements recorded since the treatment started).

The duration of overall CR is measured from the time measurement criteria are first met for CR until the first date that progressive disease is objectively documented.

Duration of stable disease: Stable disease is measured from the start of the treatment until the criteria for progression are met, taking as reference the smallest measurements recorded since the treatment started, including the baseline measurements.

6.3.5 Progression-Free Survival

PFS is defined as the duration of time from start of treatment to time of progression or death, whichever occurs first.

6.3.6 Objective Response Rate

Objective response rate (ORR) is defined as the proportion of patients with partial response or complete response.

6.3.7 Disease Control Rate

Disease control rate (DCR) is defined as the percentage of patients with partial response, complete response, or stable disease.

6.3.8 Overall Survival

Overall survival (OS) is defined as the length of time from start of treatment until death from any cause.

6.3.9 Pleural Mesothelioma

Malignant pleural mesothelioma (MPM) lesions are difficult to measure reliably.(39) Therefore, modified criteria were defined in 2004 adjusting target lesion measurements to the specific needs of this disease.

6.3.9.1 Modified RECIST Criteria for MPM

Target lesion:

Measurable at baseline and defined as tumor thickness measurements perpendicular to the chest wall or mediastinum in two positions at three separate levels on transverse cuts of CT scan. The sum of those 6 measurements define a pleural unidimensional measure. For reproducibility of lesion identification in follow up scans, cuts were taken at least 1 cm apart and close to anatomical landmarks in the thorax. Reassessments should be done at same position at the same level and by the same reader. Nodal, subcutaneous, and other measurable lesion were measured as per RECIST criteria. All unidimensional measurements were added to obtain total tumor measurement.

Evaluation of target lesions

- Complete Response (CR): Disappearance of all target lesions with no evidence of tumor elsewhere.
- Partial Response (PR): At least a 30% decrease in the total tumor measurement
- Confirmed response (PR and CR): require a repeat scan at least 4 weeks apart
- Progressive Disease (PD): At least a 20% increase in the total tumor measurement, taking as reference the smallest sum on study (this includes the baseline sum if that is the smallest on study). (Note: the appearance of one or more new lesions is also considered progression).
- Stable Disease (SD): Neither sufficient shrinkage to qualify for PR nor sufficient increase to qualify for PD, taking as reference the smallest sum diameters while on study.
- 6.3.9.2 Evaluation of Best Overall Response

The best overall response is the best response recorded from the start of the treatment until disease progression/recurrence (taking as reference for progressive disease the smallest measurements recorded since the treatment started). The patient's best response assignment will depend on the achievement of both measurement and confirmation criteria.

Abbreviated Title: LMB100 + *tofacitinib in PDA Version Date:* 08/19/20

Target Lesions	Non-Target Lesions	New Lesions	Overall Response	Best Response for this Category Also Requires:
CR	CR	No	CR	\geq 4 wks. confirmation
CR	Non-CR/Non- PD	No	PR	→ >4 wks. confirmation
PR	Non-PD	No	PR	
SD	Non-PD	No	SD	documented at least once ≥ 4 wks. from baseline
PD	Any	Yes or No	PD	
Any	PD*	Yes or No	PD	no prior SD, PR or CR
Any	Any	Yes	PD	

* In exceptional circumstances, unequivocal progression in non-target lesions may be accepted as disease progression.

Note: Patients with a global deterioration of health status requiring discontinuation of treatment without objective evidence of disease progression at that time should be reported as "*symptomatic deterioration*". Every effort should be made to document the objective progression even after discontinuation of treatment.

In some circumstances it may be difficult to distinguish residual disease from normal tissue. When the evaluation of complete response depends on this determination, it is recommended that the residual lesion be investigated (fine needle aspirate/biopsy) to confirm the complete response status.

6.4 TOXICITY CRITERIA

The following adverse event management guidelines are intended to ensure the safety of each patient while on the study. The descriptions and grading scales found in the revised NCI Common Terminology Criteria for Adverse Events (CTCAE) version 5.0 will be utilized for AE reporting. All appropriate treatment areas should have access to a copy of the CTCAE version 5.0. A copy of the CTCAE version 5.0 can be downloaded from the CTEP web site (http://ctep.cancer.gov/protocolDevelopment/electronic applications/ctc.htm)

7 NIH REPORTING REQUIREMENTS / DATA SAFETY MONITORING PLAN

7.1 **DEFINITIONS**

Please refer to definitions provided in Policy 801: Reporting Research Events found here.

7.2 OHSRP OFFICE OF COMPLIANCE AND TRAINING / IRB REPORTING

7.2.1 Expedited Reporting

Please refer to the reporting requirements in Policy 801: Reporting Research Events and Policy 802 Non-Compliance Human Subjects Research found here.

Note: Only IND Safety Reports that meet the definition of an unanticipated problem will need to be reported per these policies.

7.2.2 IRB Requirements for PI Reporting at Continuing Review

Please refer to the reporting requirements in Policy 801: Reporting Research Events found here.

7.3 NCI CLINICAL DIRECTOR REPORTING

Problems expeditiously reported to the OHSRP in iRIS will also be reported to the NCI Clinical Director. A separate submission is not necessary as reports in iRIS will be available to the Clinical Director.

In addition to those reports, all deaths that occur within 30 days after receiving a research intervention should be reported via email to the Clinical Director unless they are due to progressive disease.

To report these deaths, please send an email describing the circumstances of the death to [name] at [contact] within one business day of learning of the death.

7.4 NIH REQUIRED DATA AND SAFETY MONITORING PLAN

7.4.1 Principal Investigator/Research Team

The clinical research team will meet on a weekly basis when patients are being actively treated on the trial to discuss each patient. Decisions about dose level enrollment and dose escalation if applicable will be made based on the toxicity data from prior patients.

All data will be collected in a timely manner and reviewed by the principal investigator or a lead associate investigator. Events meeting requirements for expedited reporting as described in Section **7.2.1** will be submitted within the appropriate timelines.

The principal investigator will review adverse event and response data on each patient to ensure safety and data accuracy. The principal investigator will personally conduct or supervise the investigation and provide appropriate delegation of responsibilities to other members of the research staff.

7.4.2 Safety Monitoring Committee (SMC)

This protocol will protocol will be periodically reviewed by an intramural Safety Monitoring Committee (SMC). Initial review will occur as soon as possible after the annual NIH Intramural IRB continuing review date.

Subsequently, each protocol will be reviewed every 6 months as the quarterly meeting schedule permits or more frequently as may be required by the SMC based on the risks presented in the

study. For initial and subsequent reviews, protocols will not be reviewed if there is no accrual within the review period.

The SMC review will focus on unexpected protocol-specific safety issues that are identified during the conduct of the clinical trial.

Written outcome letters will be generated in response to the monitoring activities and submitted to the Principal investigator and Clinical Director or Deputy Clinical Director, CCR, NCI.

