The potential of LMB-100 to induce off-target vascular leak in lungs was assessed in female Wistar rats. Mild perivascular edema was reported microscopically but did not correlate with macroscopic or serum chemistry findings consistent with VLS. Ultrasound evaluation in the NHP GLP study revealed minimal accumulation of pericardial fluid with limited biological significance at the highest dose of 1 mg/kg. No appreciable accumulation of pleural fluid was observed at necropsy.

In vitro evaluation of LMB-100 in human whole blood assay indicated a low risk for cytokinemediated infusion related reaction (IRR)/cytokine release syndrome (CRS) upon first administrations. LMB-100 caused no hemolysis when added to human peripheral blood up to the highest concentrations of 0.5 mg/L.

1.2.6 Rationale for starting dose of LMB-100:

In prior Phase I study, the MTD of LMB-100 was determined to be 140 mcg/kg given as a 30minute infusion every other day x3. For this combination study, we will decrease the dose of LMB-100 to 100 mcg/kg for initial combination testing. Rationale for limitation to 3 cycles of treatment for Dose Escalation (Arm 1) and Expansion (Arm 2)

Infusion-related reaction (IRR) upon LMB-100 administration is associated with the presence of ADAs. For participant safety, treatment will be limited to 3 cycles to lower risk of IRR if tofacitinib co-treatment is unsuccessful at limiting or delaying ADA development.

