3.1.3 Treatment Extension

Participants who complete 3 cycles of therapy with LMB-100/tofacitinib and appear to be deriving clinical benefit as evidenced by lack of progression on CT scan and decreasing serum tumor marker (in patients with serum tumor marker that has historically followed their disease trend) may continue to receive additional cycles of treatment at the discretion of the PI until unacceptable toxicity or patient is no longer thought to be benefiting, or PI's decision to discontinue treatment. If a participant is offered treatment extension but refuses, he/she will be removed from protocol therapy. Participants offered treatment extension may defer immediate treatment with study drugs to take a treatment holiday or to receive other intervening treatments (including investigational treatments). If a participant chooses to defer treatment extension beyond 6 weeks or to have a different intervening therapy, the PI may require to repeat some screening safety evaluations before reinitiating LMB-100/tofacitinib and will require washout periods and criteria consistent with those described in Sections 2.1.1.8, 2.1.1.9 and 2.1.1.10. Safety monitoring while receiving treatment extension will continue as described in the Study Calendar. Limited research labs will be taken as described in Sample Collection Schedule (Section 5.2).

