3.4 STUDY CALENDAR

Unless otherwise specified, screening assessments must occur within 28 days prior to registration for study treatment. Cycle 1, day 1 assessments may occur up to 7 days prior to treatment initiation. If screening tests were performed within this window, then they do not need to be repeated on C1D1. Dosing cycles may be delayed for up to one week or started up to 2 days early to accommodate schedule conflicts, federal holidays and inclement weather, etc. They may be delayed for up to two weeks due to toxicity. There is no time limit on dosing cycle delays for patients receiving treatment extension.

			All Cycl	es (21 da	ys)					Post T	herapy
Procedure	Screening	Day 1	Day 3*	Day 4	Day 6	Day 8	Day 9	Day 15	Day 21	Safety Follow Up Visit ⁷	Long Term Follow Up ¹¹
Tofacitinib		ad	ministered	BID days	1-10 of ea	ach cycle					
Prophylactic anti- coagulation		Khorana Score < 2: administer daily on days 1-11 of each cycle Khorana Score ≥ 2: administer throughout treatment until 14 days after last dose of tofacitinib/ LMB-100									
LMB-100				Х	Х	Х					
History and PE	Х	C1 only	Х		Х	Х				Х	
Weight			Х		Х	Х	C1 only			Х	
Height			C1 only								
Vital signs ¹	Х	C1 only	Х	Х	Х	Х	C1 only			Х	
ECOG Performance Status	X	C1 only	X							Х	
Labs ²	X	C1 only	X		Х	Х		C1 only ¹⁴	C1 only ¹⁴	Х	
D-dimer		C1 only	Х			Х					
Cholesterol Panel		C1 only								Х	
TBNK		C1 only	C1 and C3 only				C1 only				
1,25-dihydroxy Vit D	Х									Х	

Abbreviated Title: LMB100 + *tofacitinib in PDA Version Date:* 08/19/20

			All Cycl	es (21 da	ys)					Post T	herapy
Procedure	Screening	Day 1	Day 3*	Day 4	Day 6	Day 8	Day 9	Day 15	Day 21	Safety Follow Up Visit ⁷	Long Term Follow Up ¹¹
Hepatitis and HIV screening panel	Х										
IGRA	Х										
Urinalysis	Х		Х		Х	Х				Х	
Urine albumin and creatinine	C1 only		C1 only		C1 only	C1 only					
Pregnancy test ³	Х		Х								
Confirmation of Dx ⁴	Х										
Assessment of tumor MSLN expression ^{4, 5}	X										
CT CAP and/or MRI ⁸	X	•	cles of stud	•		days				Х	Х
CA 19-9-or appropriate tumor-specific marker ⁵			Х							X	
Doppler U/S of bilateral lower extremities		Optional ¹⁵									
ECG	X		C1 only			C1 only				X	
Echocardiogram	Х										
Ambulatory Oxygen Saturation	Х										
Chest X-ray			X ⁹								
NIH Advance Directives Form ⁶		C1 only ⁶									
Biopsy	X ¹³	C1 only ¹²	C2 only 12								

Abbreviated Title: LMB100 + tofacitinib in PDA *Version Date:* 08/19/20

			All Cycl	es (21 da	ys)					Post T	herapy

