This evaluation in 15 patients of either histology (but at least 8 patients in this expansion phase must have pancreatic adenocarcinoma) will be undertaken using the following guidelines: The objective will be to determine if the fraction of patients who are able to achieve threshold levels of LMB-100 in cycle 2 is consistent with 80% and greater than 50%. If 15 evaluable patients are enrolled, and if 11 or more patients meet threshold drug levels in cycle 2, then the probability of this occurring is 5.9% if the true probability of achieving threshold drug levels in cycle 2 were 50% and the probability of this occurring is 83.6% if the true probability of achieving threshold drug levels in cycle 2 were 80%. Thus, the expansion phase would be considered to have a positive outcome if 11 or more of 15 patients in the expansion phase achieve threshold drug levels. In practice, after the trial has ended accrual, the fraction of evaluable patients assessed during the expansion phase that achieve threshold drug levels in cycle 2 will be determined and reported along with two-sided 80% and 95% confidence intervals to aid in interpretation of the results. The fraction of patients who achieve threshold drug levels in cycle 3 will also be reported along with a 95% confidence interval, but this may be a small fraction and will be interpreted as being an exploratory evaluation.

As an early stopping rule, if after the first 5 evaluable patients in the expansion cohort have been treated, 0 of the 5 achieve threshold drug levels in cycle 2, then no further patients will be accrued as soon as that can be determined, with no pause in accrual, since this would be inconsistent with the goal of having 11 or more of 15 patients achieving threshold drug levels in cycle 2.

With up to 12 patients in the dose escalation phase and 15 in the expansion cohort, a maximum of 27 evaluable patients are required to complete accrual to this study. The accrual ceiling will be set at 45 patients to account for screen failures or patients who are treated but unable to complete the DLT period. It is anticipated that up to two patients per month may enroll onto this trial. Thus, accrual is expected be completed in approximately 2 years.

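### Scheduled Safety Monitoring Committee review depends on accrual, so it can lapse while participants are still dosed in the uncapped treatment extension

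*Combined protocol and SAP*

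**What the plan says.** Section 7.4.2 sets the SMC timetable. On the first review it says: "Initial review will occur as soon as possible after the annual NIH Intramural IRB continuing review date". After that, "each protocol will be reviewed every 6 months as the quarterly meeting schedule permits or more frequently as may be required by the SMC". It then adds the limiting sentence: "For initial and subsequent reviews, protocols will not be reviewed if there is no accrual within the review period". The condition is enrolment. The section does not mention whether anyone is still being dosed.

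Section 3.1.3 says that participants who finish three cycles and appear to benefit "may continue to receive additional cycles of treatment at the discretion of the PI until unacceptable toxicity", loss of benefit, or a decision by the investigator to stop. It gives no maximum number of cycles. It also lets participants defer extension for a treatment holiday or for another therapy, which may itself be investigational, and then return. Section 3.4 adds: "There is no time limit on dosing cycle delays for patients receiving treatment extension".

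Section 1.2.6 gives the reason for the three-cycle limit in both arms. Infusion-related reactions (IRRs) are associated with anti-drug antibodies (ADAs), and "treatment will be limited to 3 cycles to lower risk of IRR" in case tofacitinib does not hold ADAs back. Extension is the stated exception to that limit.

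**The concern.** A safety committee's calendar should follow exposure, and this one follows recruitment. The two coincide while the trial is enrolling and separate afterwards, when extension cycles may be the only dosing left.

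Those cycles have little prior human experience. Table 6 gives a total of 1 of 13 earlier patients with expected LMB-100 levels in cycle 3. Its rows as printed add to 2 of 15, but either count is small. Extension is also planned: section 1.1.3 lists ADA prevention beyond three cycles as an exploratory objective. At stake is whether a committee that meets on a fixed calendar sees late-cycle toxicity, or whether someone must first raise a concern.

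**Working it through.** **1. The plan's own accrual figures (section 10.2).** Evaluable maximum: 6 × 2 + 15 = 27, as stated. The ceiling is 45. At the stated maximum of two per month, 45 / 2 = 22.5 months, which agrees with "Thus, accrual is expected be completed in approximately 2 years". By contrast, 27 / 2 = 13.5 months does not. The stated rate and duration therefore belong with the ceiling of 45.

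**2. The SMC calendar on that timeline.** Assume that the annual clock and enrolment start together and that reviews are held on time. Scheduled reviews then fall at about months 12, 18 and 24. The last enrolment is at about month 22.5 (maximum rate) to month 24. The period from month 18 to 24 contains accrual and is reviewed. The period from month 24 to 30 contains none, so its review is cancelled, as is each later one.

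**3. Where extension falls.** Three 21-day cycles take 63 days, or 63 / 30.4 = 2.1 months. For the last enrolled participant, cycle 4 starts at the earliest at:
- 22.5 + 2.1 = month 24.6 (maximum rate), or
- 24 + 2.1 = month 26.1 (full two years).

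Both fall after the month-24 review, so all of that participant's extension cycles lie in periods with no scheduled SMC review. For earlier participants, extension cycles given before month 24 are covered and later ones are not.

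**4. How this depends on the date of last enrolment.** Take a six-month period as 26 weeks. Without delays, cycle k starts 3(k − 1) weeks after enrolment. If the last enrolment is on the first day of a period, cycle 9 starts at week 24 (inside) and cycle 10 at week 27 (outside). If it is on the last day, cycle 2 onward lies outside. Deferrals push cycles later, and section 3.4 does not limit them, so the documents set no upper bound on how long dosing may continue after the last scheduled review.

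**5. Whether another rule schedules a committee look at those cycles.**
- *IMC (section 7.4.3).* One scheduled meeting, once five subjects have finished the DLT window. Later meetings are ad hoc, called by the principal investigator or requested by the IRB or SMC if concerns arise. The principal investigator is one of its three members.
- *1/6 rule (section 10.4.4).* It counts DLTs, which section 3.1.1 confines to the first 21-day cycle, and it decides only whether enrolment goes on. It does not see cycle 4 toxicity and has no effect once accrual has ended.
- *Weekly meetings (section 7.4.1).* These follow dosing, not accrual, but they are held by the study team.
- *Study Calendar monitoring, SAE reporting and IRB continuing review (sections 3.1.3, 3.4, 8.3 and 7.2.2).* All continue without an accrual condition. None is the periodic SMC review that section 7.4.2 sets up.

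None of these schedules a monitoring-committee meeting for extension cycles given after the last reviewed period.

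**The case against.** The strongest reply is that the SMC is one layer among several. A reader might infer that extension dosing after accrual goes unreviewed. The documents do not support that: the team meets weekly while anyone is on treatment, Study Calendar monitoring continues in extension, SAEs are reported within 24 hours, IRB continuing review carries no accrual condition, and the IMC can be convened at any time. This stands, and it confines the point to scheduled SMC review. The SMC may also ask for more frequent review, but the no-accrual sentence follows that provision and makes no exception to it.

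A reader might also infer from the late first SMC review that 24 of 27 patients (89%) could be treated before it, since "It is anticipated that up to two patients per month may enroll onto this trial" and 2 × 12 = 24. This does not hold as a fraction. The 24 is an upper bound on enrolment, which section 10.2 allows to include screen failures, while 27 counts evaluable patients. On the two-year timeline, month 12 sees 45 / 24 × 12 = 22.5 of 45 enrolled, or 27 / 24 × 12 = 13.5 of 27 evaluable: half in each case. The IMC also looks first. At the maximum rate the fifth subject finishes the DLT window at about day 82 to 94, with about six patients started, roughly nine months before the annual date. Moving the first SMC review to the end of escalation would partly duplicate that look, and I do not propose it.

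A third inference is that review stops as soon as a stopping rule closes accrual. A period that contains any accrual is still reviewed, so the lapse begins with the next one.

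Finally, few participants may be affected. Section 10.2 expects that as many as 50% may progress by restaging after two cycles, and section 10.4.9 calls the extension group a small subset. That limits the size of the gap but does not close it.

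**Conclusion.** The point holds in a limited form. From the first review period after the one containing the last enrolment, section 7.4.2 provides no scheduled SMC review, although sections 3.1.3 and 3.4 allow dosing to continue or restart without a cap or time limit. On the plan's own timeline this reaches every extension cycle of the last enrolled participant, and any extension cycle given to others after about month 24.

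This rests on reading accrual as enrolment, on six-monthly reviews held on time, and on the annual clock starting with enrolment. A different start date or a late meeting moves the onset but does not remove the gap. The documents do not give the expected number of extension participants, so I put no figure on patients affected. This is a weakness in a design choice and a cheap improvement to oversight. It does not question the extension itself or its clinical rules.

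**What to change.** In section 7.4.2, change the condition for skipping a review so that a period is skipped only *if no participant was accrued or received study drug* during it. The rest of the SMC timetable can stay as written.

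The cost is one sentence and a few additional six-monthly reviews of a small data set by an existing committee. No dose, endpoint or sample size changes. The section's wording speaks of protocols in general, so the sentence may be a standing committee rule. In that case the sponsor would need to agree a protocol-specific exception with the SMC.
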